#### 7.8.1 Adverse Events

AEs will be coded with the most recent version of MedDRA.

The analyses of AEs will be descriptive in nature. All analyses of AEs will be based on the number of subjects with AEs and not on the number of AEs.

For further details on summarization of AE data, please refer to "Analysis and Presentation of Adverse Event Data from Clinical Trials" (7) and "Handling of missing and incomplete AE dates" (3).

The analysis of AEs will be based on the concept of treatment emergent AEs. That means that all AEs will be assigned to screening or on-treatment phase as defined in Section 6.1. AEs will be analysed based on actual treatments, as defined in Table 6.1: 1.

An overall summary of AEs will be presented. This overall summary will comprise summary statistics for the class of AESIs.

#### **CTP Section 5.2.6.1.4:** *The following are considered as AESIs:*

#### • *Hepatic injury*

A hepatic injury is defined by the following alterations of hepatic laboratory parameters:

- An elevation of AST (aspartate transaminase) and/ or ALT (alanine transaminase) ≥3-fold ULN combined with an elevation of total bilirubin ≥2fold ULN measured in the same blood sample, or
- $\circ$  Aminotransferase (ALT, and/ or AST) elevations  $\geq 10$  fold ULN

The investigator had to classify on the eCRF whether an observed AE was an AESI or not.

According to ICH E3 (8), in addition to deaths and SAEs, "other significant" AEs need to be listed in the clinical trial report. These will be any non-serious adverse event that led to an action taken with study drug (e.g. discontinuation or dose reduced or interrupted).

The frequency of subjects with AEs will be summarised by treatment, primary SOC and preferred term. AEs which were considered by the investigator to be drug related will be summarised separately. Separate tables will also be provided for subjects with SAEs and subjects with AESIs. AEs will also be summarized by maximum intensity.

The SOCs and preferred terms within SOCs will be sorted by descending frequency over all treatment groups.

For disclosure of AE data on ClinicalTrials.gov, the frequency of subjects with non-serious AEs occurring with an incidence of greater than 5 % (in preferred terms) will be summarised by treatment, primary SOC and preferred term. The frequency of subjects with SAEs will also be summarised.

For disclosure of AE data in the EudraCT register, the frequency of AEs, the frequency of non-serious AEs with an incidence of greater than 5 % (in preferred terms) and the frequency of SAEs will be summarized.

For support of lay summaries, the frequency of subjects with drug-related SAEs will be summarized by treatment, primary SOC and preferred term.

#### 7.8.2 Laboratory data

The analyses of laboratory data will be descriptive in nature and will be based on BI standards "Display and Analysis of Laboratory Data" (9).

Analyses will be based on normalised values, which mean transforming to a standard unit and a standard reference range. The original values will be analysed if the transformation into standard unit is not possible for a parameter.

Descriptive statistics of absolute values and change from baseline from laboratory parameters over time (see Section 6.7) will be provided. Frequency tables of changes between baseline and last value on treatment with respect to the reference range will be presented.

Unscheduled measurements of laboratory data will be assumed to be repeat measurements of the most recent scheduled measurement (e.g. for follow-up or confirmation of a particular value). Therefore, unscheduled measurements will be assigned to the planned time point of the previous scheduled measurement. Descriptive statistics will be calculated by planned time point based on the worst value of the subject at that planned time point (or assigned to that planned time point).

Possibly clinically significant abnormal laboratory values are only those identified either in the Investigator's comments or at the RPM at the latest. It is the Investigator's responsibility to decide whether a lab value is clinically significant abnormal or not. Standard or project-specific rules for flagging clinically significant values in an automated manner will not be applied in this study.

Clinically relevant findings in laboratory data will be reported as baseline conditions (prior to first administration of study treatment) or as AEs (after first administration of study treatment) if judged clinically relevant by the investigator, and will be analyzed as such.

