5.2.3 Safety laboratory parameters

For the assessment of laboratory parameters, blood and urine samples will be collected by the trial site at the times indicated in the [Flow Chart](#). For all safety laboratory sets A and B, subjects should be fasted for at least 10 h. For retests, at the discretion of the investigator or designee, overnight fasting is not required.

The parameters that will be determined are listed in Tables [5.2.3: 1](#) and [5.2.3: 2](#). Reference ranges will be provided in the ISF, Section 10.

Manual differential white blood cell count or urine sediment examinations will only be performed, if there is an abnormality in the automatic blood cell count or in the urinalysis, respectively.

Proprietary confidential information © 2020 Boehringer Ingelheim International GmbH or one or more of its affiliated companies

Table 5.2.3: 1

Routine laboratory tests

Functional lab group	BI test name [comment/ abbreviation]	A	B
Haematology	Haematocrit Haemoglobin Red Blood Cell Count/ Erythrocytes White Blood Cells/ Leucocytes Platelet Count/ Thrombocytes (quant)	X X X X X	X X X X X
Automatic WBC differential, relative	Neutrophils; Eosinophils; Basophils; Monocytes; Lymphocytes	X	X
Automatic WBC differential, absolute	Neutrophil, absol.; Eosinophils, absol.; Basophils, absol.; Monocytes, absol.; Lymphocytes, absol.	X	X
Manual differential WBC (if automatic differential WBC is abnormal and clinically relevant in the opinion of the investigator)	Neut. Poly (segs); Neut. Poly (segs), absol.; Neutrophils Bands; Neutrophils Bands, absol.; Eosinophils/ Leukocytes; Eosinophils, absol.; Basophils/ Leukocytes; Basophils, absol.; Monocytes/ Leukocytes; Monocytes, absol.; Lymphocytes/ Leukocytes; Lymphocytes, absol.		
Coagulation	Activated Partial Thromboplastin Time Prothrombin Time – INR (International Normalization Ratio)	X X	X X
Enzymes	AST [Aspartate transaminase]/ GOT, SGOT ALT [Alanine transaminase]/ GPT, SGPT Alkaline Phosphatase Gamma-Glutamyl Transferase	X X X X	X X X X
Hormones	Thyroid Stimulating Hormone	X	--
Substrates	Glucose (Plasma) Creatinine Bilirubin, Total Bilirubin, Direct (only if bilirubin above upper limit normal) Protein, Total C-Reactive Protein (Quant)	X X X X X X	X X X X X X
Electrolytes	Sodium Potassium Calcium Chloride	X X X X	X X X X

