#### 6. GENERAL ANALYSIS DEFINITIONS

#### 6.1 TREATMENTS

For basic study information on treatments to be administered, assignment of treatment groups, and selection of doses, cf. Section 4 of the CTP.

The trial is divided into two parts but only trial part 1 was performed.

In **trial part 1**, each subject is planned to be treated in five subsequent treatment periods (five-period cross-over) with one single dose in each treatment period followed by one single dose in a sixth treatment period in a fixed sequence.

Treatments in the five-period cross-over:

- Reference treatment 1 (R1) 60mg tab IR fasted: 60 mg of BI 894416, IR tablets under fasted conditions
- Test treatment 1 (T1) 62.5mg tab FRR fasted:
   62.5 mg of BI 894416, ER tablet (fast release rate) under fasted conditions
- Test treatment 2 (T2) 62.5mg tab SRR fasted:
   62.5 mg of BI 894416, ER tablet (slow release rate) under fasted conditions
- Test treatment 3 (T3) 62.5mg cap FRR fasted:
   62.5 mg of BI 894416, ER capsule (fast release rate) under fasted conditions
- Test treatment 4 (T4) 62.5mg cap SRR fasted:
   62.5 mg of BI 894416, ER capsule (slow release rate) under fasted conditions

Each subject is planned to be randomly allocated to one of five treatment sequences (T3-R1-T1-T4-T2, T2-T1-T3-R1-T4, T4-T3-R1-T2-T1, T1-T4-T2-T3-R1 and R1-T2-T4-T1-T3, cf. Table 6.1: 2).

Treatments in the fixed sequence:

- Test treatment 5 (T5) 62.5mg tab SRR fed:
   62.5 mg of BI 894416 ER, tablet (slow release rate) after a high fat breakfast
- Test treatment 6 (T6) 62.5mg cap SRR fed:
   62.5 mg BI 894416, capsule (slow release rate) after a high fat breakfast

Subject will be randomly allocated to either T5 or T6, stratified by sequence (cf. Table 6.1: 2 for an overview of the treatment sequences).

For statistical analysis of AEs, safety laboratory data and vital signs, the following analysis phases are defined for each subject:

Table 6.1: 1 Flow chart of analysis phases for statistical analyses of AEs

Study analysis phase	Label	Start (inclusive)	End (exclusive)
Screening	Screening	Date of informed consent	Date/time of administration of BI 894416 in any formulation
On-treatment	BI 894416 respectively	Date/time of administration of BI 894416 in any formulation	Date/time of administration of BI 894416 in another formulation or 12:00 a.m. on day after subject's trial termination date, whichever occurs earlier

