Analysis phases for statistical analysis of AEs are defined for each subject as described in the table above.

CTR Section 15, Appendix 16.1.13.1.8.2 and Appendix 16.1.13.1.8.3 AE displays will present results for the on-treatment phase only.

In disposition, demographics and baseline characteristics, all subjects will be analysed together (i.e., one "BI 894416" column). Exposure will be summarised by period and treatment formulation.

The statistical analyses of safety laboratory tests and vital signs will be performed including all subject together (i.e., one "BI 894416" column), with clear differentiation between baseline (cf. Section 6.7) and on-treatment measurements.

Table 6.1: 2 Overview of treatment sequences

Trial part 1
T3-R1-T1-T4-T2-T5
T3-R1-T1-T4-T2-T6
T2-T1-T3-R1-T4-T5
T2-T1-T3-R1-T4-T6
T4-T3-R1-T2-T1-T5
T4-T3-R1-T2-T1-T6
T1-T4-T2-T3-R1-T5
T1-T4-T2-T3-R1-T6
R1-T2-T4-T1-T3-T5
R1-T2-T4-T1-T3-T6

More details on the technical implementation of these analyses are provided in the ADS Plan of this TSAP.

TSAP for BI Trial No: 1371-0022

Proprietary confidential information © 2021 Boehringer Ingelheim International GmbH or one or more of its affiliated companies

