#### 6.7 BASELINE, TIME WINDOWS AND CALCULATED VISITS

Baseline is defined as the last available value before any administration of BI 894416 (in any formulation).

Time windows are defined in Section 6.1 of the CTP. Adherence to time windows will be checked at the RPM.

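### The laboratory shift table rests on the end-of-trial sample, 7 to 14 days after the last dose, so it cannot show a change at 24 to 72 h that has since resolved

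*SAP*

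**What the plan says.** **Shift table.** SAP 7.8.2 plans it as follows: "Frequency tables of changes between baseline and last value on treatment with respect to the reference range will be presented". SAP 6.1 defines the phases and gives their scope: "For statistical analysis of AEs, safety laboratory data and vital signs, the following analysis phases are defined for each subject". In SAP Table 6.1: 1 the on-treatment phase ends at the next formulation or at "12:00 a.m. on day after subject's trial termination date, whichever occurs earlier". The table has only a screening and an on-treatment phase. On display, SAP 6.1 says: "The statistical analyses of safety laboratory tests and vital signs will be performed including all subject together", in a single BI 894416 column. SAP 6.7 takes as baseline the last value before the first dose of any formulation.

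**Protocol phases.** Protocol 7.3.4 closes the treatment period at the end of the residual effect period (REP) and assigns later data to follow-up, leaving the detailed intervals to the SAP. SAP section 4 declares all its analyses to be in accordance with the revised protocol.

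**Descriptive statistics.** SAP 7.8.2 also plans absolute values and changes from baseline over time. Unscheduled measurements are moved to the preceding scheduled time point, and the statistics are "based on the worst value of the subject at that planned time point". Protocol 5.2.3 requires a 10 h fast for the scheduled sets but adds: "For retests, at the discretion of the investigator or designee, overnight fasting is not required". For vital signs, SAP 7.8.3 only lists unscheduled values.

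**The concern.** Safety laboratory tests are a named safety parameter (protocol 2.2.2.2, SAP 5.3.2). Protocol 1.4.3 expects any effect on immune cells to be transient and relies on white cell count, differential count and CRP to monitor it. A shift table read one to two weeks after the last dose is poorly placed to show such a change.

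The table also has a role that no other planned laboratory output fills. SAP 7.8.2 switches off automated flagging of clinically significant values, so this is the only planned laboratory summary that counts subjects against the reference range without investigator or meeting judgement. The by-time means and the listings do not count how many subjects moved out of range after dosing.

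The secondary question is whether repeats distort the means. Baseline takes the last pre-dose value, while each later time point takes the worst. An abnormal value that normalises on repeat therefore disappears at baseline but is kept after dosing. The repeat may also be non-fasted.

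**Working it through.** There is no power or alpha figure to reproduce: the sample size is not based on a power calculation (protocol 7.7) and the laboratory analysis is descriptive.

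**1. Which sample is the last on-treatment value?** Inputs are the part 1 flow chart (dosing on Day 1; EoT visit on Day 8 to 15 with laboratory set A) and SAP Table 6.1: 1 with its pooled column. I read the EoT day as counted from Day 1 of the last period. This is an inference, but no other reading fits doses that may be only 4 days apart.
- Earliest EoT: 8 − 1 = 7 days = 168 h after the last dose.
- Latest EoT: 15 − 1 = 14 days = 336 h after the last dose.

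The on-treatment phase runs past this visit, so for a completer the EoT sample is the last value. A subject who stops early without an EoT visit contributes an earlier sample.

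**2. How much does the table leave out?** Scheduled samples after the first dose, per completer:
- pre-dose in periods 2 to 6: 5
- 24 h after each of six doses: 6
- 72 h, before discharge in the last period only: 1
- EoT: 1
- total: 5 + 6 + 1 + 1 = 13

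The table uses 1 of 13, and none of the 6 + 1 = 7 samples taken 24 to 72 h after a dose. Thyroid stimulating hormone is an exception to the argument. It belongs to set A only, so it has no 24 h or 72 h value to omit.

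**3. Would a by-treatment reading rescue it?** No. If a last value were taken within each treatment phase, the pre-dose sample of the next period (drawn within 3 h before dosing) would still belong to the preceding phase. It lies at least 4 × 24 − 3 = 93 h after the preceding dose, so the 24 h samples would still not be used.

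**4. Would the protocol's phases alone rescue it?** Only in part. If EoT counted as follow-up, the pooled last value would still be a single sample from period 6, and the 24 h samples of the first five periods would stay out.

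**5. Size of the worst-value effect on the means.** The documents give no repeat rate, so the rates here are assumptions. If a fraction f of subjects has one repeat unrelated to the first value, the time-point mean shifts by f × SDw/√π, where SDw is the within-subject SD and 1/√π = 0.564.

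| Subjects repeated, of 24 | Shift in mean (SDw) |
|---|---|
| 1 | 0.02 |
| 2 | 0.05 |
| 4 | 0.09 |
| 6 | 0.14 |

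SAP 7.8.2 describes repeats as following up or confirming a value, so a high first value is the likelier trigger. Simulating that (2.5 to 10% repeated, intra-subject correlation 0.5 to 0.9, both assumed), the repeat is the worse value in about 9 to 35% of repeated cases. The mean then exceeds the scheduled-value mean by 0.001 to 0.010 total SD. These figures exclude any systematic food effect, for which the documents give no size. With no repeat, the rule changes nothing.

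**The case against.** The early post-dose data are not lost. The by-time statistics cover all seven 24 to 72 h samples, every value is listed, out-of-range values are highlighted (protocol 7.3.4), and clinically relevant findings become adverse events, with hepatic injury tabulated separately. This stands. A reader might infer that both laboratory outputs measure the wrong thing, and the documents do not support that. The shift table answers a narrower question, status at the end of the trial, and a change that persists to EoT does appear in it.

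A reader might also infer that the means are pushed towards a spurious effect. That is not shown either. The rule acts only where a repeat exists and is worse, a non-fasted repeat is permitted rather than prescribed, and taking the worst value is a conservative safety convention. The direction of worst for analytes that can be abnormal both ways may be set in the sponsor's laboratory standard, which SAP 7.8.2 cites and which is not available here, so its absence from the SAP cannot be called a gap.

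The REP length is in protocol 1.2.3, outside the text available for this review, so it cannot be confirmed that Day 8 to 15 falls after it. The 4-day washout separates doses; nothing says laboratory effects resolve within it. Protocol 7.3.4 also lets the SAP define the intervals. These points limit the charge to a follow-up phase that the protocol describes and the SAP omits without comment.

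Replacing the last value with the lowest and highest over all draws would be a poor remedy. With a 95% reference range and independent draws (assumed), the chance of at least one out-of-range value in seven is 1 − 0.95^7 = 30%, or about 24 × 0.30 = 7 of 24 subjects, against 24 × 0.05 = 1.2 for one draw. Within-subject correlation lowers the 30% but does not remove the inflation. This objection is accepted and shapes the fix.

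**Conclusion.** The point holds for the shift table. For completers it reports laboratory status 7 to 14 days after the last dose and cannot show a reference-range shift at 24 to 72 h after any of the six doses that has resolved by EoT. This rests on the phase definitions and pooled display in SAP 6.1, on the EoT day being counted from the last dosing day, and on the cited laboratory standard not redefining the last on-treatment value.

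The worst-value rule is a minor, secondary matter: 0.001 to 0.010 total SD for triggered repeats, and 0.02 to 0.14 within-subject SD for random ones, under assumed repeat rates.

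Importance is low to moderate. The tables are descriptive, come from 24 healthy men, and touch neither PK endpoint. The change is worth making because it is cheap and lets the table show transient changes.

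**What to change.** 1. In SAP 7.8.2, present the reference-range shift tables by planned post-dose time point: 24 h in each period and 72 h in the last period. Show low and high separately and give EoT its own column.
2. Reconcile the phases in SAP Table 6.1: 1 with the REP and follow-up split in protocol 7.3.4, or declare the difference in SAP section 4.
3. Secondary: base the means and changes from baseline on the scheduled, fasted sample and list unscheduled repeats, as SAP 7.8.3 does for vital signs.

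The cost is SAP wording and a re-run of standard tables on existing data. There are three downsides. The tables have more cells. Some out-of-range counts will arise by chance across several time points (about 1 of 24 subjects per analyte and time point under the 95% range assumption), and a footnote should say so. Repeats leave the means and appear only in listings.

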Statistical methods	Preliminary pharmacokinetic analyses and simulations will be performed between trial part 1 and trial part 2A as, well as between part 2A and 2B, if appropriate. Relative bioavailability will be estimated by the ratios of the geometric means (test/reference) for primary, secondary and further selected endpoints. Additionally, their two-sided 90% confidence intervals (CIs) will be provided. This method corresponds to the two one-sided t-test procedure, each at a 5% significance level. Since the main focus is on estimation and not testing, a formal hypothesis test and associated acceptance range is not specified. The statistical model will be an analysis of variance (ANOVA) on the logarithmic scale. CIs will be calculated based on the residual error from the ANOVA. Descriptive statistics will be calculated for all endpoints.

FLOW CHART – TRIAL PART 1

Period	Visit	Day	Planned time (relative to drug administration) [h:min]	Approximate clock time of actual day [h:min]	Event and comment	Safety laboratory ⁷	PK blood	Neurological examination ⁸	12-lead ECG	Vital signs (BP, PR)	Questioning for AEs and concomitant therapy ⁶
SCR	1	-28 to -1			Screening (SCR) ¹	A		x	x	x	
1/2/3/4/5/6 (six periods separated by a wash-out of at least 4 days)	2/3/4/5/6/7	-1	-12:00	20:00	Admission to trial site (visit 2 only)	x ⁵					x
			-11:30	20:30	Snack (voluntary)						
		1	-1:30	06:30	Allocation to treatment ² (visit 2 only)	B ^{2/9}	x ²		x ²	x ²	x ²
			-0:30	07:30	High fat, high calorie breakfast (Treatment T5 & T6 only)						
			0:00	08:00	Drug administration (with 240 mL fluid intake)						
			0:20	08:20			x				x
			0:40	08:40			x				x
			1:00	09:00			x		x	x	x
			2:00	10:00	240 mL fluid intake		x		x	x	x
			3:00	11:00			x				x
			4:00	12:00	240 mL fluid intake, thereafter lunch ³		x		x	x	x
			5:00	13:00			x				x
			6:00	14:00			x				x
			8:00	16:00	Snack (voluntary) ³		x		x	x	x
			10:00	18:00			x				x
			11:00	19:00	Dinner						
			12:00	20:00			x				x
			14:00	22:00			x				x
			16:00	24:00			x				x
		2	24:00	08:00		B	x		x	x	x
			34:00	18:00			x				x
		3	48:00	08:00			x				x
			58:00	18:00			x				x
		4	72:00	08:00	Breakfast (voluntary) Discharge from trial site (visit 7 only)	B ¹⁰	x		x	x	x
EoT	8	8 to 15			End of trial (EoT) examination ⁴	A		x	x	x	x

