1. Subject must be informed and written informed consent obtained prior to starting any screening procedures. Screening procedures include physical examination, check of vital signs, ECG, safety laboratory (including drug screening, alcohol breath- and urine cotinine test), demographics (including determination of body height and weight, smoking status and alcohol history), relevant medical history, concomitant therapy and review of inclusion/exclusion criteria.
2. The time is approximate; the procedure is to be performed and completed within the 3 h prior to drug administration.
3. If several actions are indicated at the same time, the intake of meals will be the last action.
4. At the end of trial visit the EoT examination includes physical examination, vital signs, ECG, safety laboratory, recording of AEs and concomitant therapies.
5. Only urine drug screening and alcohol breath test will be done at this time.
6. AEs and concomitant therapies will be recorded throughout the trial, but will be specifically asked for at the times indicated in the [Flow Chart](#) above.
7. A and B define different sets of safety laboratory examinations (see Section [5.2.3](#))

Proprietary confidential information © 2020 Boehringer Ingelheim International GmbH or one or more of its affiliated companies

8. Unscheduled neurological examinations may be added at any time during the trial for individual volunteers or the whole treatment group, e.g., in case of neurological adverse events, if assessed as necessary by the investigator.
9. Pharmacogenetic samples will be collected at Day 1 prior to first drug administration in period 1.
10. Only to be taken before discharge from the trial site

FLOW CHART – TRIAL PARTS 2A & 2B (OPTIONAL)

Period	Visit	Day	Planned time (relative to drug administration) [h:min]	Approximate clock time of actual day [h:min]	Event and comment	Safety laboratory ⁷	PK _{blood}	Neurological examination ⁸	12-lead ECG	Vital signs (BP, PR)	Questioning for AEs and concomitant therapy ⁶
SCR	1	-28 to -1			Screening (SCR) ¹	A		x	x	x	
1/2/3/4/5 (five identical periods separated by a wash-out of at least 4 days – preliminary PK analysis between periods 3 and 4)	2/3/4/5/6	-1	-12:00	20:00	Admission to trial site (visit 2 only)	x ⁵					x
			-11:30	20:30	Snack (voluntary)						
		1	-1:30	06:30	Allocation to treatment ² (visit 2 only)	B ^{2/9}	x ²		x ²	x ²	x ²
			-0:30	07:30	High fat, high calorie breakfast (Treatments T8 & T10 only)						

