5.2.6.1.4 Adverse events of special interest

The term adverse events of special interest (AESI) relates to any specific AE that has been identified at the project level as being of particular concern for prospective safety monitoring and safety assessment within this trial, e.g. the potential for AEs based on knowledge from other compounds in the same class. AESIs need to be reported to the sponsor's Pharmacovigilance Department within the same timeframe that applies to SAEs, refer to Section [5.2.6.2.2](#).

The following are considered as AESIs:

- **Hepatic injury**
A hepatic injury is defined by the following alterations of hepatic laboratory parameters:
 - An elevation of AST (aspartate transaminase) and/ or ALT (alanine transaminase) ≥ 3 -fold ULN combined with an elevation of total bilirubin ≥ 2 -fold ULN measured in the same blood sample, or
 - Aminotransferase (ALT, and/ or AST) elevations ≥ 10 fold ULN

These lab findings constitute a hepatic injury alert and the subjects showing these lab abnormalities need to be followed up according to the 'DILI checklist' provided in the ISF or eDC system, as applicable. In case of clinical symptoms of hepatic injury (icterus, unexplained encephalopathy, unexplained coagulopathy, right upper quadrant abdominal pain, etc.) without lab results (ALT, AST, total bilirubin) available, the Investigator should make sure that these parameters are analysed, if necessary in an unscheduled blood test. Should the results meet the criteria of hepatic injury alert, the procedures described in the DILI checklist should be followed.

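### SAP 7.8.2 files an unscheduled laboratory sample taken 0-24 h after a dose in the pre-dose row of the by-time-point summary, at odds with the date/time phases in SAP 6.1

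*SAP*

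**What the plan says.** SAP 7.8.2 treats all unscheduled laboratory samples alike: "Unscheduled measurements of laboratory data will be assumed to be repeat measurements of the most recent scheduled measurement". It follows that "unscheduled measurements will be assigned to the planned time point of the previous scheduled measurement". The summary rule is then: "Descriptive statistics will be calculated by planned time point based on the worst value of the subject at that planned time point", which the SAP extends to values assigned to that time point. Nothing is said about a dose falling between the two samples.

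The part 1 Flow Chart schedules laboratory set B at -1:30 and at 24:00 in each period. Footnote 2 fixes the first of these before the dose: "the procedure is to be performed and completed within the 3 h prior to drug administration". A further set B appears at 72:00, but footnote 10 restricts it: "Only to be taken before discharge from the trial site", and discharge is at visit 7.

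SAP 6.1 defines analysis phases that also cover laboratory data, with on-treatment beginning at the date and time of administration. It says the laboratory analysis will be done "with clear differentiation between baseline (cf. Section 6.7) and on-treatment measurements". SAP 6.7 takes baseline as the last value available before any BI 894416 is given.

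**The concern.** A repeat sample confirms an earlier value only if nothing relevant happened in between. Here the trial dose can lie between the two samples. An early unscheduled sample may well be drawn because of something seen after dosing. The protocol foresees one such case in Section 5.2.6.1.4: where there are clinical symptoms of hepatic injury and no liver results, "the Investigator should make sure that these parameters are analysed, if necessary in an unscheduled blood test".

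Under 7.8.2 that result would appear in the table as a pre-dose value. A reader of the by-time-point summary would see the abnormality before the dose and nothing corresponding after it. The table would point the wrong way on the question it exists to answer, namely whether laboratory values change after dosing.

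**Working it through.** The plan has no figure to reproduce here. The check applies the written rule to the written schedule.

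**1. Inputs.** Scheduled laboratory times in part 1 are -1:30 and 24:00 in every period, plus 72:00 in period 6 (Flow Chart and its footnotes 2 and 10). The planned number of subjects is 24 (Protocol 7.7). I read the visit 2 restriction in the -1:30 row as applying to treatment allocation, not to the laboratory sample.

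**2. Filing rule.** Filed time = the latest scheduled time at or before the sample.

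| Unscheduled sample (h after dose) | Filed at |
|---|---|
| 0.5, 4, 8, 16, 23.9 | -1:30 (pre-dose) |
| 30, 48, 71 | 24:00 |

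The result is the same in periods 1-5 and in period 6. Every sample in the first 24 h after a dose is filed before that dose.

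**3. Worst-value rule.** Taking high as worse, the tabulated pre-dose value for the subject is max(true pre-dose value, unscheduled value). The SAP does not define the direction of worst for parameters that can be abnormal on either side.

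**4. Illustration, all laboratory values assumed.** Each of 24 subjects has a true pre-dose value of 20, and one has an unscheduled sample u at 8 h. If u exceeds 20, the tabulated pre-dose mean is (23 × 20 + u)/24 = 20 + (u - 20)/24.

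| u | Value tabulated as pre-dose | Pre-dose mean | Pre-dose maximum |
|---|---|---|---|
| 10 or 20 | 20 | 20.00 | 20 |
| 40 | 40 | 20 + 20/24 = 20.83 | 40 |
| 60 | 60 | 20 + 40/24 = 21.67 | 60 |
| 120 | 120 | 20 + 100/24 = 24.17 | 120 |
| 200 | 200 | 20 + 180/24 = 27.50 | 200 |

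In the first line of the table the sample leaves no trace in the summary. In the others it becomes the pre-dose maximum. In no line does it enter the 24 h row.

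**5. Comparison with SAP 6.1.** By clock time an 8 h sample belongs to the on-treatment phase of the formulation just given. By planned time point, 7.8.2 places it before that administration. In period 1 this crosses the boundary between baseline and on-treatment. In periods 2-6 the pre-dose sample is itself on-treatment, in the phase of the preceding formulation, so the value moves from after one dose to before it. The SAP does not say which rule prevails.

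**The case against.** The strongest reply is that the SAP defines baseline by time of administration, so little of consequence can go wrong. Much of this stands.

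- **Baseline is safe.** A reader might infer that change from baseline is corrupted. Suppose (assumed values) pre-dose 25, 150 at 6 h and 120 at 24 h. Subtracting tabulated time-point values gives 120 - 150 = -30. The SAP does not plan that subtraction. It refers to the Section 6.7 baseline, which a post-dose sample cannot be, so the planned change is 120 - 25 = +95. The shift tables use the same baseline. The documents do not support a claim that the reference value is inflated.
- **Periods 2-6 touch no baseline.** There, and with all laboratory data pooled in one BI 894416 column, the error moves a value between two on-treatment rows. The row is still wrong relative to the dose, and Section 6.7 has no bearing on it.
- **The protocol does not call for a test after any early symptom.** Section 5.2.6.1.4 concerns symptoms of hepatic injury without results available, and then only if necessary.
- **The finding is not hidden.** Individual values are listed, clinically relevant findings are reported as adverse events, and hepatic injury has its own table as an event of special interest. A reader might infer that a safety signal would be lost altogether; it would not.
- **Unseen documents may help.** The sponsor's laboratory display standard and the ADS Plan might contain a dose condition. That is possible, but an explicit rule in the SAP should not depend on an unseen document overriding it.

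The reply does not remove the core point: the text of 7.8.2 places a post-dose value in a pre-dose row.

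**Conclusion.** The concern holds in a limited form. As written, 7.8.2 puts any unscheduled laboratory sample from the first 24 h after a dose in the pre-dose row, in all six periods of part 1. The sample displaces the true pre-dose value only when it is worse, and otherwise disappears from the summary. This conflicts with the phases in SAP 6.1.

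The consequence is a wrong row in descriptive laboratory tables. Baseline, and with it the reference side of the change and shift tables, is intact. The pharmacokinetic endpoints are unaffected. The size depends on how many such samples exist, which the documents do not state; with none, nothing changes. The means shown above rest on assumed values and only illustrate the mechanism. The correction is nonetheless worth making, because this is an explicit rule giving a wrong result, not an omitted detail, and it costs almost nothing to mend.

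**What to change.** Add to SAP 7.8.2 that an unscheduled sample is assigned to the previous scheduled time point only if no administration of BI 894416 lies between the two, and that a sample taken after a dose is never assigned to a time point before that dose.

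Then choose one treatment for such samples:

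- assign them to the next scheduled post-dose time point of the same period (24 h); or
- list them only, as SAP 7.8.3 already does for unscheduled vital signs.

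The first keeps the value in a post-dose summary, but under the worst-value rule it may displace the true 24 h value. Listing only avoids that, at the price of leaving the value out of the summary.

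The cost is one sentence in the SAP and one date/time condition in the laboratory program, with no new data. Since the SAP records that part 1 has been performed, listing any unscheduled samples dated within 24 h after a dose would show whether any table is affected.
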